## **Study Protocol:**

The patients were inducted from the Out Patient Department of Endodontics in Baqai Dental College Hospital Karachi, Pakistan. A non-probability consecutive sampling was done and 120 patients were included and randomly divided in the 4 groups (n=30) using simple randomization as per the inclusion criteria. The study size was calculated with reference to previous reports, revealing that at least 30 individuals should be included as per the analysis of power of the study. The value of power used was 0.96, the effect size was taken as 0.4, and  $\alpha$  was set as 0.05. A verbal informed consent was taken from each participant before including them in a group.

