### **Inclusion Criteria:**

- Patients between the ages of 18 - 65 years.
- Patients with no medical or systemic conditions.
- Patients with prolonged pain response on cold pulp testing of 1st and 2nd mandibular molars.
- Patient with 1st and 2nd mandibular molars having symptomatic irreversible pulpitis with no periapical pathology or tenderness on percussion.
- Preoperative moderate to severe pain on Heft Parker's visual analogue scale.
- Patients who can understand the recording of the pain using Heft Parker's visual analogue scale.

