### **Exclusion criteria:**

- Patients who are pregnant and/or breastfeeding.
- Patients with reported allergy to diclofenac sodium, piroxicam, and tramadol.
- Patients with periodontal pathologies, necrotized pulp, ankylosed or resorbed roots, open apex and non-restorable tooth.
- Patients who have taken an analgesic in the past 24 hours.

The study was designed to be a double blinded study, where the operators and the patients both were unaware of the groups of drugs that were used; this anonymity was achieved by marking the groups A, B, C and D on boxes for drugs containing a placebo, diclofenac sodium, piroxicam, and tramadol respectively. The Heft Parker's visual analogue scale was used to assess

the patients' pain levels prior to the drug ingestion, and the study was continued on the patients that reported moderate to severe pain on the visual analogue scale. On this scale, the pain intensities were categorized as: no pain (0), mild pain (1-54 mm), moderate pain (55- 114 mm) and severe pain (> 114 mm). The patients were then given their respective group of drug where the control group received vitamin E (Evion, 400 mg) and three experimental groups received one tablet/capsule of diclofenac sodium (Voltral SR100, 100 mg), piroxicam (Feldene, 20 mg), and tramadol (Tramal, 50 mg). The patients were instructed to wait for 1 hour before they were administered inferior alveolar nerve block with 1.8 ml of 2% lidocaine with 1:100000 epinephrine using a non-aspirating syringe through a long needle of 27-Gauge. Standard root canal treatment was initiated after lip numbness was achieved, and pain levels were reassessed by Heft Parker's visual analogue scale during the root canal procedure. However, the patients who did not achieve the numbness of the lips were excluded from the study. Patients who reported discomfort and pain during the endodontic procedure were intervened appropriately; conversely, if the patient did not report any intraoperative pain, endodontic procedure was resumed.

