### **Statistical Analysis Plan:**

Test of normality was checked using one sample Shapiro Wilk. One-way ANOVA with Tukey's post-hoc will be employed if parametric test criteria is met; however, if the parametric criteria was not fulfilled, the experimental groups will be compared using Kruskal–Wallis test with post-hoc analysis. The Chi-square test will be used to compare gender and drug groups against the IANB efficacy. These aforementioned tests were conducted on SPSS Statistics version 25 (IBM Corp., Armonk, NY, USA).

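### IANB efficacy is tested by unadjusted chi-square: the drug test is valid but forgoes the precision that pre-drug pain would give, and the non-randomised gender p-value needs adjustment and an exploratory label

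*SAP*

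**What the plan says.** The SAP (Statistical Analysis Plan) deals with the success outcome in one sentence: "The Chi-square test will be used to compare gender and drug groups against the IANB efficacy". It names no stratified test, regression model or baseline covariate. It does not say whether the gender table combines the four arms, but a single chi-square with no stratification reads most naturally that way. Nor does it say whether the gender result is descriptive or is meant as an effect of gender.

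On allocation, the Protocol (Study Protocol) says "120 patients were included and randomly divided in the 4 groups (n=30) using simple randomization as per the inclusion criteria". No stratification by gender or pain is stated. Patients enter consecutively ("A non-probability consecutive sampling was done"), so gender is observed and not assigned.

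Starting pain is known for everyone because it is an entry condition: "Preoperative moderate to severe pain on Heft Parker's visual analogue scale" (Inclusion Criteria). The text under Exclusion criteria divides the eligible range into "moderate pain (55- 114 mm) and severe pain (> 114 mm". No analysis in the SAP is stated to use this score.

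**The concern.** Two comparisons of different standing share one sentence, one test and no label. Drug group is randomised; gender is not. A reader would tend to give the two p-values equal weight.

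For the drug comparison, the stake is precision. A baseline score that probably predicts intraoperative pain is collected and then left out, so the test has less power than the same data allow.

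For gender, the stake is interpretation. Entry at 55 mm or more narrows the range of starting pain but leaves both moderate and severe pain. If men and women differ within that range, and starting pain lowers the chance of success, the crude table can show a gender difference when gender has no effect beyond starting pain.

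**Working it through.** **1. The plan's own figure.** The inputs from the Protocol (Study Protocol) are four groups of 30, "The value of power used was 0.96, the effect size was taken as 0.4", and alpha, which "was set as 0.05". Reading the effect size as Cohen's f, a one-way ANOVA has noncentrality λ = f²N = 0.4² × 120 = 19.2 on 3 and 116 df. Power is 0.964, against the stated 0.96, and 30 is the smallest group size that reaches 0.96. A 3-df chi-square with w = 0.4 and the same λ gives 0.970. The sizing therefore covers a four-group comparison. None is stated for gender.

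**2. Assumed inputs.** The documents give no success rates, gender split, pain distribution or pain-success relation. The scenarios assume:
- 120 patients, half of them women, and no gender effect beyond starting pain;
- drug log-odds 0/0.9/0.9/0.9 with placebo intercept -0.4, which at average pain is 1/(1+e^0.4) = 40% success on placebo and 1/(1+e^-0.5) = 62% on each drug;
- odds of success multiplied by 0.67, 0.50 or 0.37 per SD of pre-drug HP-VAS;
- a gap of 0.3 or 0.5 SD in pre-drug HP-VAS between women and men.

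Each simulated trial compared the crude Pearson chi-square with a likelihood-ratio test from a logistic model containing drug, gender and pre-drug HP-VAS.

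**3. Drug test (3 df).** Crude power was 26-38% and adjusted power 33-40%, a gain of about 2 to 8 points depending on the scenario. Type I error after adjustment was near 5-6%, so a small part of the gain may reflect a slightly liberal likelihood-ratio test.

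This effect is smaller than the planned one. The mean success rate is (0.401 + 3 × 0.622)/4 = 0.567, and w² = [0.25 × (0.401 - 0.567)² + 0.75 × (0.622 - 0.567)²]/(0.567 × 0.433) ≈ 0.037, so w ≈ 0.19. If the true effect were w = 0.4, crude power would already be 0.97 and adjustment could add at most 3 points.

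**4. Gender test, continuous starting pain.** The crude test rejected in about 7-20% of trials and the adjusted test in about 5-6%. The mildest odds factor, 0.67, gave only 6-8% for the crude test. The upper end needs both the larger gap and the steepest factor.

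**5. Gender test, pain as two categories.** A second design assumed success of 0.30/0.60/0.60/0.50 by arm and 8,000 trials per scenario. It compared the crude test with Cochran-Mantel-Haenszel (CMH) tests.

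| Severe pain, men v women | Odds reduction with severe pain | Crude | CMH by drug | CMH by drug and pain |
|---|---|---|---|---|
| no difference | none | 5.2% | 5.1% | 5.1% |
| 40% v 60% | 2-fold | 7.2% | 6.8% | 5.0% |
| 40% v 60% | 3-fold | 9.0% | 8.6% | 5.2% |
| 30% v 60% | 3-fold | 14% | 14% | 4.7% |
| 30% v 70% | 4-fold | 29% | 29% | 5.3% |

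Stratifying by drug alone changes almost nothing; stratifying by pain as well restores the 5% level. The excess comes from starting pain, not from drug mix.

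**6. Drug mix in a single trial.** With 60 men and 60 women, the SD of the difference in placebo share is √(0.25 × 0.75 × 2/60) = 7.9 points. A 1.96-SD imbalance is 15.5 points. With 0.30 success on placebo and (0.60 + 0.60 + 0.50)/3 = 0.567 on the drugs, it shifts the gender difference by 0.155 × 0.267 ≈ 4 points and lifts the conditional rejection rate to about 7%. Over all randomisations the rate is about 5%.

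**The case against.** Much of the case for leaving the plan alone is sound.

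- **Drug mix.** A reader might infer that unequal drug mix between men and women can pass as a gender effect. Drug is randomised independently of gender, so imbalance arises only by chance, which the test's error rate already covers. This stands.
- **The drug test.** A reader might infer that ignoring gender under simple randomisation biases the drug comparison. It does not: with no drug effect and an assumed 25-point gender effect, the crude drug chi-square rejected in 5.1% of trials. The largest gap in the share of women between any two arms averages 19 points and is 20 or more in about 49% of trials, but that is the worst of six pairs. For one given drug against placebo, the mean gap is 10 points and 20 or more occurs in 15.5%. Even a 20-point gap moves that contrast by 0.20 × 25 = 5 points, about 0.4 of its standard error of √(2 × 0.25/30) ≈ 13 points. This stands; the argument for adjusting the drug test is precision only.
- **What the gender test claims.** The plan makes no causal claim. If women start with more pain and succeed less often for that reason, the crude association is real. Starting pain may also lie on the path from gender to outcome, and adjusting for it then asks a different question. This stands, and it is why the gender term should be labelled exploratory and not presented as a corrected effect.
- **Size of the remedy.** Labelling the gender table would be enough if gender were the only issue. It would leave unused a baseline score that every patient provides and that helps the randomised comparison, so this part does not dispose of the point.

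**Conclusion.** The point holds as one of precision and labelling. The crude drug chi-square is valid. Using pre-drug HP-VAS would raise its power by about 2 to 8 points under the assumed effects, and by 3 at most if the effect is as large as the sample-size statement supposes. The crude gender p-value calls for caution: under assumed pain gaps of 0.3 to 0.5 SD and no gender effect of its own, it falls below 0.05 in about 7-20% of trials, against about 5-6% after adjustment. If men and women start with equal pain, or pain hardly affects success, the excess disappears.

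The documents do not support the stronger conclusions that the drug comparison is biased, that drug mix inflates the gender test, or that the plan sets out to report a causal gender effect. The stated sample size is unaffected.

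**What to change.** Analyse IANB efficacy by one logistic regression on drug group (four levels), pre-drug HP-VAS as a continuous covariate, and gender. Take the drug result from the 3-df test in that model. Report the gender term as exploratory, with a sentence that starting pain may mediate rather than confound it. Keep the crude drug and gender tables as description. The model takes efficacy as a yes/no outcome. The documents do not define it, so the same SAP paragraph should do so.

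The cost is a change of SAP wording and one standard SPSS procedure, with no new data and no change in sample size. The drawback is that the odds ratios are conditional on the covariates and differ from those in the crude tables, so adjusted success percentages by drug group should be shown beside them.

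### HP-VAS pain and an undefined IANB efficacy outcome can each show a drug effect and neither is primary, so the chance of a false positive is above the nominal 5%: roughly 7–8%, or 8–11% with the cut-off left open

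*SAP*

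**What the plan says.** **Error rate and size.** The Protocol, under Study Protocol, gives alpha once, as an input to the sample size: it "was set as 0.05". The same paragraph says "The value of power used was 0.96, the effect size was taken as 0.4", and that "120 patients were included and randomly divided in the 4 groups (n=30) using simple randomization". It names no outcome, no test and no type of effect size.

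**Outcomes.** The procedure text that follows the Exclusion criteria says "pain levels were reassessed by Heft Parker's visual analogue scale during the root canal procedure". It divides the scale into "no pain (0), mild pain (1-54 mm), moderate pain (55- 114 mm) and severe pain (> 114 mm". These are bands for describing pain and for selecting patients; none is called a success rule. The same text separates patients who had pain during treatment, who were managed, from those who had none, whose treatment carried on.

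**Analyses.** The SAP says "One-way ANOVA with Tukey's post-hoc will be employed if parametric test criteria is met", with Kruskal–Wallis and post-hoc comparisons otherwise. It does not name the variable. It then says "The Chi-square test will be used to compare gender and drug groups against the IANB efficacy". Neither document names a primary outcome, ranks the two analyses or adjusts for having both, and neither defines IANB efficacy.

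**The concern.** Two analyses can each produce a statement that the drugs differ, and nothing says which one carries the conclusion. If either may do so, the chance of at least one false positive is the chance that any of them crosses 0.05, which is larger than 5%.

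The missing definition of efficacy adds to this. Two analysts could both follow the SAP, one counting only a score of 0 as success and the other counting scores up to 54 mm, and report different success rates and different chi-square p-values from the same patients. Both the headline outcome and the success rule could then be settled after the results are known, and a reader could not tell whether that had happened.

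**Working it through.** **1. The plan's own figure.** Inputs from the Protocol: 4 groups, N = 4 × 30 = 120, effect size 0.4, alpha 0.05, stated power 0.96.

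- *0.4 read as Cohen's f, one-way ANOVA.* Noncentrality λ = f²N = 0.16 × 120 = 19.2, with 3 and 116 degrees of freedom. The probability that a noncentral F exceeds its 5% critical value is **0.964**. With 29 per group (N = 116) it is 0.958, so 30 is the smallest group size that reaches 0.96.
- *0.4 read as Cohen's w, chi-square on a 4 × 2 table.* λ = w²N = 19.2 again, with (4 − 1)(2 − 1) = 3 degrees of freedom. Power is **0.970**.

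The stated 0.96 is reproduced most closely by the ANOVA reading, but the chi-square reading is near it too.

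**2. Bounds for the false-positive rate.** For two tests at 0.05:

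- independent: 1 − 0.95² = 0.0975
- upper bound whatever the correlation: 0.05 + 0.05 = 0.10

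Two tests with one fixed cut-off therefore cannot exceed 10%. A higher figure needs a third test, that is, a free choice of cut-off.

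**3. Simulation with no drug effect.** Both outcomes are taken from the same scores, so they are correlated and the true rate lies below the independent figure. The documents give no HP-VAS distribution, so one has to be assumed: normal scores rounded to whole millimetres and clipped to 0–170 mm, four groups of 30, no exclusions, 20,000 trials per setting. The Monte Carlo standard error near 8% is √(0.08 × 0.92 / 20,000) = 0.0019, or 0.2 percentage points. The last three columns give the chance of at least one p < 0.05.

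| Mean / SD (mm) | Score 0 | Score ≤54 | Kruskal–Wallis or chi-square at 54 mm | Any of Kruskal–Wallis, 54 mm, 0 mm | Same, with ANOVA |
|---|---|---|---|---|---|
| 60 / 45 | 9.3% | 45.1% | 7.6% | 10.8% | 11.1% |
| 30 / 40 | 23.1% | 73.0% | 7.8% | 11.1% | 11.4% |

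- Over means of 40–80 mm and SDs of 40–45, the rate is 7.2–8.2% with the 54 mm cut-off fixed and 9.9–11.1% with the cut-off open.
- At mean 100 and SD 40, zeros are rare, so the 0 mm rule adds little, and the open-cut-off rate is 8.1%.
- With ANOVA in place of Kruskal–Wallis the open-cut-off rate runs slightly higher, up to 11.8% in one run.

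**4. Where the excess comes from.** Alone, Kruskal–Wallis and the 54 mm chi-square each give 4.5–5.2%, and the 0 mm chi-square gives 2.4–5.0%. No single test is faulty; the excess comes from having several unranked routes.

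**5. What is not counted.** The gender chi-square is not a test of drug effect. Post-hoc pairwise comparisons are left out because they follow the omnibus test.

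**The case against.** **The sample size already shows that HP-VAS leads.** A reader might infer that the power statement fits only the continuous comparison. The documents do not support that. The Protocol names no test or effect-size type, and the chi-square reading gives 0.970 against ANOVA's 0.964. The inference leans towards HP-VAS without settling it, and nothing in the SAP demotes the chi-square.

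**The plan promises no trial-wide 5%.** This stands. A reader might say that the trial breaks a stated 5% error rate, but 0.05 is only a sample-size input. Applying it to each test, and taking HP-VAS as the variable for ANOVA or Kruskal–Wallis, are both inferences. They are reasonable ones, because no other alpha and no other continuous outcome after dosing is described.

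**Nothing says that either result alone would count as a drug effect.** Also true, so the figures are conditional on that. The plan does not rule it out either.

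**The figures depend on assumed scores.** They do, and narrow intervals would be falsely precise. A reader might also attribute 11% to the two outcomes alone; the 10% bound shows that it needs the open cut-off as well.

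**The success rule can be read from the Protocol.** A reader might take 54 mm as the rule because it is the upper limit of mild pain. The procedure text leans the other way, since treatment carried on where no pain was felt, which suggests 0 mm. That text describes conduct and does not define an outcome. A chi-square across all four pain bands is a further possible reading.

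**Conclusion.** The concern holds in conditional form. If each test is judged at 0.05 and either could support a drug effect, the chance of at least one false positive is above the nominal 5%: roughly 7–8% with the cut-off fixed at 54 mm, and 8–11% with it open between 0 and 54 mm. This rests on clipped-normal scores with mean 30–100 mm and SD 40–45, and on 30 analysed per group.

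The inflation is moderate and does not invalidate the trial. The absence of a definition of efficacy is a defect whatever the exact rate, because the plan as written does not determine which patients count as successes. The documents do not establish which outcome was meant to lead or which cut-off was meant.

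**What to change.** Before analysis, amend the SAP to:

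1. **Name one primary outcome and test at 0.05.** The four-group comparison of intraoperative HP-VAS is the natural choice, because 0.4 read as f comes closest to the stated power. The sponsor should confirm which outcome and effect-size type were intended.
2. **Define IANB efficacy once, on HP-VAS.** The sponsor should choose between 0 mm and 0–54 mm and reconcile the choice with the Protocol's text on patients with and without pain during treatment.
3. **Order the tests.** Test the other outcome formally only if the primary is significant. With no drug effect, a false claim then requires a false positive on the primary, which returns the rate to about 5%.
4. **Label the gender comparison exploratory.**

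The cost is SAP wording, with no added patients or measurements. The small downside is that no confirmatory claim can be made on the secondary outcome if the primary is not significant.
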